6 STUDY DESIGN

7 SELECTION OF STUDY POPULATION

This study will enroll 14 middle-aged, healthy males and females with mildly elevated LDL. Each participant must fulfill the inclusion criteria and not meet any of the exclusion criteria as described in Sections 7.1 and 7.2, respectively.

7.1 Inclusion Criteria

1. Provided voluntary, written, informed consent to participate in study
 2. Males and females between 30 and 55 years of age
 3. BMI between 20.0 to 29.9 kg/m², inclusive
 4. Female participant is not of child-bearing potential, defined as females who have undergone a sterilization procedure (e.g. hysterectomy, bilateral oophorectomy, bilateral tubal ligation, total endometrial ablation)
- Or,
- Females of child-bearing potential must have a negative baseline urine pregnancy test and agree to use a medically approved method of birth control for the duration of the study. Acceptable methods of birth control include:
- Non hormonal contraceptives
 - Double-barrier method
 - Intrauterine devices

- Non-heterosexual lifestyle or agrees to use contraception if planning on changing to heterosexual partner(s)
 - Vasectomy of partner at least 6 months prior to screening
5. Subjects with mid-range (2.5–4.1mmol/L or 100-159 mg/dL) elevated LDL-C levels
 6. Agrees to maintain current level of physical activity throughout the study
 7. Willingness to complete all questionnaires, records, and diaries and assessments associated with the study and to complete all clinic visits.
 8. Healthy as determined by medical history, laboratory results, and as assessed by Qualified Investigator (QI)

7.2 Exclusion Criteria

1. Women who are pregnant, breast feeding, or planning to become pregnant during the course of the trial
2. Women who are menopausal or post-menopausal
3. Currently following a diet (i.e. Ketogenic Diet, low-carbohydrate diet)
4. Subjects with high TSH level (>4.5mU/L) or Self reported pre-existing thyroid condition. Treatment on a stable dose of medication for at least 3 months will be considered by the QI
5. Participants with type I or II Diabetes Mellitus
6. Cancer, except skin cancers completely excised with no chemotherapy or radiation with a follow up that is negative. Volunteers with cancer in full remission for more than five years after diagnosis are acceptable.
7. Participants with previous or current pathology of the pancreas
8. Current or history of Gastroesophageal reflux disease (GERD) or any significant disease of the gastrointestinal tract
9. Self reported hypertension or on hypertensives.
10. Significant cardiovascular event in the past 6 months as assessed by the QI.
11. Major surgery in the past 3 months or individuals who have planned surgery during the course of the trial. Participants with minor surgery will be considered on a case-by-case basis by the QI
12. Gastric bypass surgery
13. Individuals with an autoimmune disease or are immune-compromised
14. Self reported HIV-, Hepatitis B- and/or C-positive diagnosis
15. History of or current diagnosis with kidney and/or liver diseases as assessed by the QI on a case-by-case basis, with the exception of history of kidney stones symptom free for 6 months
16. Self reported medical or neuropsychological condition and/or cognitive impairment that, in the QI's opinion, could interfere with study participation
17. Self reported blood/bleeding disorders as per QI
18. Current use of prescribed medications listed in Section 7.3.1
19. Current use of over-the-counter medications, supplements, foods, and/or drinks listed in Section 7.3.2
20. Alcohol or drug abuse within the last 12 months
21. High alcohol intake (>2 standard drinks per day or >10 standard drinks per week)
22. Clinically significant abnormal laboratory results at screening as assessed by the QI
23. Blood donation 30 days prior to screening, during the study, or a planned donation within 30-days of the last study visit
24. Participation in a clinical research trial within 30 days of study initiation

25. Individuals who are unable to give informed consent
26. Any other active or unstable medical condition, that, in the opinion of the QI, may adversely affect the participant's ability to complete the study or its measures or may pose significant risk to the participant

7.3 Concomitant Medications

Participants who are taking any prescribed medications that are considered not to affect the study outcomes must agree to maintain their current dosing regimen during the study unless otherwise recommended by their family physician.

7.3.1 Prescribed Medications

Participants on the following concurrent prescribed medications and/or treatments will be excluded during enrollment unless they have been taken off these therapies by their family physician. In the latter event, the frequency of use and/or dosage may be considered by the QI on a case by case basis prior to recommending an appropriate washout or their enrollment in the study.

1. Corticosteroids (pills, nasal sprays, injections)
2. Hormonal Medication (contraceptives)
3. Opioid pain medications
4. Beta blockers and Blood pressure medications (clonidine, propranolol)
5. Statins
6. Selective serotonin reuptake inhibitors (SSRIs)

7.3.2 Over-the-counter Medications, Supplements and Foods/Drinks

Participants who are currently consuming the following over-the-counter (OTC) Medications, supplement and food/drinks will not be allowed to participate unless willing to undergo a 14-day washout period prior to their baseline visit and agree not to take the supplements during the study. Other OTCs supplement and food/drinks will require a case-by-case assessment by the QI based on dose and/or frequency of use to determine adequate washout.

1. NSAIDs, with the exception of ibuprofen
2. Calcium supplements
3. Protein supplements
4. Orlistat
5. Caffeine supplements
6. Carbohydrate boosting Supplements
7. Exogeneous ketone supplements
8. Supplements known to affect weight and/or fat loss or lipid metabolism, including but not limited to:
 - a. Omega 3 and 6 supplements
 - b. Hemp seed oil supplement
 - c. Flaxseed oil supplement

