5 STUDY OBJECTIVES

The objective of this study is to investigate the efficacy of Nic's Ketogenic Diet on cardiovascular health and inflammation in healthy adults with mildly elevated LDL-C.

Primary outcomes:

The change in inflammation, as assessed by the change in erythrocyte sedimentation rate (ESR) and C-reactive protein (CRP) following Nic's Keto Diet for 140 days. The main outcome of the study is to investigate whether in periods of higher LDL there will be positive impacts on cardiovascular health and inflammation.

Secondary outcomes:

Changes to the following parameters from baseline to day 140 at monthly intervals following Nic's Keto Diet:

1. Weight
2. Blood pressure (BP)
3. Lipid panel

Changes to the following parameters from baseline to days 70 and 140 following Nic's Keto Diet:

1. Body composition (total body fat (%), android fat (%), gynoid fat (%), android/gynoid fat ratio, and muscle mass (%)) as assessed by DEXA Scan

[figure not shown]
Changes to the following parameters from baseline to day 140 following Nic's Keto Diet:

1. HbA1c
2. Fasting glucose
3. Free Tri-iodothyronine (T3)

Safety outcomes:

1. Incidence of pre-emergent and post-emergent adverse events
2. Electrocardiogram (ECG) after 70 and 140 days of following Nic's Keto Diet
3. Vital signs: heart rate (HR)
4. Anthropometrics: BMI calculation
5. Clinical chemistry: alanine aminotransferase (ALT), aspartate aminotransferase (AST), total bilirubin, creatinine, electrolytes (Na⁺, K⁺, Cl⁻, P), HbA1c, fasting glucose, and estimated glomerular filtration rate (eGFR))
6. Hematology: white blood cell (WBC) count with differential (neutrophils, lymphocytes, monocytes, eosinophils, basophils), red blood cell (RBC) count, hemoglobin, hematocrit, platelet count, RBC indices (mean corpuscular volume (MCV), mean corpuscular hemoglobin (MCH), mean corpuscular hemoglobin concentration (MCHC), red cell distribution width (RDW), and mean platelet volume (MPV))

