9.2 Visit 2 – Baseline (Day 0)

Eligible participants will return to the clinic for baseline assessments after a 12-hour fast.

Baseline (Day 0) assessments include:

1. Collection and review of food records
2. Assessment of inclusion and exclusion criteria

3. Physical exam
4. Review of concomitant therapies and adverse events
5. Urine pregnancy test for female potential participants that are of child-bearing potential
6. Weight measurements and BMI calculation (Section 9.5.1)
7. Seated resting blood pressure and heart rate measurements (Section 9.5.2)
8. Total body DEXA scan
9. Collection of fasted blood for analysis of glucose, HbA1c, C-reactive protein, lipid panel, Free tri-iodothyronine (T3), and ESR.
10. Deliver Nutrition Counselling about Nic's Keto Diet (Section 9.7.7)
11. Dispense Nic's Keto Diet e-book
12. Dispense glucose and ketone monitors and instruct participants on their use. First fasted ketone and glucose measure to be taken with monitors during baseline clinic visit.
13. Dispense or assign dates of 3-day food records
14. Dispense participant treatment diary and instruct participants on use

The next visit will be scheduled for day 28.

Reminders for participants prior to their next in-clinic visit:

1. Return to the clinic in a 12-hour fasted state
2. Complete 3- day food records weekly. Weekly records will be reviewed by nutrition team and counselling provided as required.
3. Participants will receive a 2-week follow up email from Nutrition Team (Section 9.7.7).
4. Abide by instructions for medications as per Section 7.3.1 and OTC medications, supplements, and food and drinks as per Section 7.3.2.
5. Complete subject treatment diary
6. Maintain similar physical activity and study diet
7. Monitor glucose and ketones daily

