9.5 Visits 6-7 (Day 84, 112 ± 3 days)

Participants will return to the clinic after a 12-hour fast to complete assessments for Visits 6-7 with completed food records and subject treatment diary.

Assessments for Visits 6-7 include:

1. Collection and review of subject treatment diary
2. Collection and review of food records
3. Compliance calculation
4. Review of concomitant therapies and adverse events
5. Collection of fasted ketone and glucose and review of glucose and ketone monitors
6. Seated resting blood pressure and heart rate measurements
7. Weight measurement and BMI calculation (Section 9.5.1)
8. Collection of blood sample for lipid panel analysis (Section 9.5.2)
9. Dispense or assign dates of 3-day food records
10. Re-dispense subject treatment diary

The next visit will be scheduled for day 140

Reminders for participants prior to their next in-clinic visit:

1. Return to the clinic in a 12-hour fasted state
2. Complete 3-day food records weekly. Weekly records will be reviewed by nutrition team and counselling provided as required.
3. Abide by instructions for medications as per Section 7.3.1 and OTC medications, supplements, and food and drinks as per Section 7.3.2.
4. Complete subject treatment diary
5. Maintain similar physical activity and study diet
6. Monitor glucose and ketones daily

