9.6 Visit 8 – End-of-Study (Day 140 ± 3 days)

Participants will return to the clinic after a 12-hour fast to complete end of study assessments with completed food records and subject treatment diary.

Visit 8 assessments include:

1. Collection and review of subject treatment diary
2. Collection and review of food records
3. Compliance calculation
4. Collection and review of glucose and ketone monitors
5. Collection of fasted ketone and glucose and review of glucose and ketone monitors
6. Review of concomitant therapies and adverse events
7. Weight measurements and BMI calculation (Section 9.5.1)
8. Seated resting blood pressure and heart rate measurements (Section 9.5.2)
9. Total body DEXA scan and ECG
10. Urine pregnancy test for female potential participants that are of child-bearing potential
11. Collection of fasted blood samples for the analysis of CBC, electrolytes (Na⁺, K⁺, Cl⁻, P), HbA1c, eGFR, creatinine, AST, ALT, total bilirubin, fasting glucose, C-reactive protein, lipid panel, free tri-iodothyronine (T3), and ESR

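### Ibuprofen is exempt from the NSAID restriction, with no fixed ibuprofen-free interval before the only two CRP and ESR draws and no planned output showing recent use

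*Combined protocol and SAP*

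**What the plan says.** Section 7.3.2 lists over-the-counter items that require a 14-day washout before baseline. The first item reads "NSAIDs, with the exception of ibuprofen", so the fixed washout does not reach ibuprofen. OTC products not on the list are left to a "case-by-case assessment by the QI based on dose and/or frequency of use to determine adequate washout", with no fixed interval and no stated time point.

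The primary outcome in Section 5 is the change in ESR and CRP over 140 days. Both are drawn at Visit 2 (Section 9.2: "Collection of fasted blood for analysis of glucose, HbA1c, C-reactive protein, lipid panel", with ESR at the end of the same item) and at Visit 8 (Section 9.6: "total bilirubin, fasting glucose, C-reactive protein, lipid panel, free tri-iodothyronine (T3), and ESR"). Visits 3 to 7 draw a lipid panel only.

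The reminder before Visit 8, in Section 9.5, tells participants to follow the rules for "OTC medications, supplements, and food and drinks as per Section 7.3.2"; Section 9.1 carries the same reminder before Visit 2. Neither adds anything on ibuprofen. Participants on permitted prescribed drugs "must agree to maintain their current dosing regimen during the study" (Section 7.3), but no such rule covers OTC ibuprofen.

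Every visit includes a check of concomitant therapies (Section 1.3; at Visit 8, "Review of concomitant therapies and adverse events"). The model in Section 11.3 contains baseline value and visit only. Section 11.4 lists protocol deviations.

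**The concern.** The primary outcome is a before-after change in two markers that the protocol itself uses to measure inflammation. Each is measured once before and once after the diet, and no comparator is described. The plan restricts other NSAIDs but allows one anti-inflammatory by name, without a reason and without a fixed interval before either draw.

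Steady use at both draws would largely cancel in the change. Use near one draw only would not, if the drug or the complaint behind it affects CRP or ESR. A lowering near Day 140 could be read as a diet benefit, and a lowering near Day 0 could hide one. A complaint that raises the markers would reverse both.

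The planned outputs could not show whether this had happened. There is no intermediate CRP or ESR value to compare with, the model has no term for use, no listing of concomitant therapies against results is planned, and permitted ibuprofen would not normally appear among protocol deviations.

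**Working it through.** **Text check.** Four places could supply an ibuprofen-free interval.

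- *Fixed washout (7.3.2):* 14 days before baseline, for listed items. Ibuprofen is excepted.
- *QI clause (7.3.2):* covers OTC products not listed. It may reach ibuprofen at baseline. The word washout suggests entry, but the sentence carries no time limit and later reminders refer back to 7.3.2. Its reach at Day 140 is therefore unclear.
- *Reminders (9.1, 9.5):* point back to 7.3.1 and 7.3.2 and give no interval.
- *Visit 8 preparation (9.6):* a 12-hour fast, food records and the diary. Nothing on analgesics.

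No fixed interval precedes either draw.

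**Illustration of size.** The plan has no figure to reproduce: Section 11.1 sets 14 participants without a calculation. From the documents: n = 14 and two-sided alpha 0.05. Assumed, because the documents are silent: each affected participant's change moves by r = 0 to 1.5 SD of the paired change, and the number affected varies. A paired t-test on normal changes stands in for the planned MMRM, since CRP and ESR have one post-baseline value each (simulation, 4,000,000 runs per case).

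For scale, the observed mean change needed for p < 0.05 is t(0.975, 13)/√14 = 0.577 SD, and the change detectable with 80% power is 0.81 SD.

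Let a be the number shifted down and b the number shifted up. Bias in the mean change = -(a - b) × r/14.

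- a = 1, r = 0.25: -0.25/14 = -0.02 SD.
- a = 3, r = 1.5: -4.5/14 = -0.32 SD.

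Two-sided error with no diet effect:

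| Affected | r = 0.25 | r = 0.5 | r = 1.0 | r = 1.5 |
|---|---|---|---|---|
| a = 1 | 5.0% | 5.0% | 5.0% | 4.95% |
| a = 2 | 5.1% | 5.4% | 6.3% | 7.3% |
| a = 3 | 5.3% | 6.1% | 8.7% | 11.8% |
| a = 1, b = 1 | 4.9% | 4.6% | 3.7% | 2.6% |
| a = 2, b = 2 | 4.8% | 4.3% | 2.7% | 1.3% |

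At r = 0 the error is 5.0%. By symmetry, the two-sided figures are the same if all affected participants shift up instead. With a = 1 the total does not rise, but it tilts: the lower tail is 2.9/3.2/3.8/4.3% and the upper tail 2.1/1.8/1.2/0.7% across the four values of r.

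Power for a true decrease of 0.8 SD is 79.0% with nobody affected. With b = 1 it is 77.1/74.8/68.8/61.2%, and with b = 2 it is 75.1/70.1/57.5/42.1%.

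**The case against.** The strongest reply is that the link to the endpoint is not in the documents. No section says that ibuprofen, or any NSAID, changes CRP or ESR, and 7.3.2 gives no reason for restricting NSAIDs. Effect, number of users and timing are all assumed. This stands, and the point can only be conditional.

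Direction is also open. Someone who starts ibuprofen shortly before Day 140 has a reason, and that complaint could itself raise the markers. The net shift could be nil or upward. This stands too. A reader might infer that the exemption favours the diet or inflates the false-positive rate; the documents do not support that. The table shows what assumed shifts would do and is not evidence that they occur.

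A reader might also infer that nothing governs ibuprofen before Day 140. That is too firm, because the QI clause has no stated time limit.

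Use near Day 140 may be uncommon. Participants are healthy, autoimmune disease is excluded, and headache, the listed diet effect most likely to prompt an analgesic, is described as short-term in Section 13.3. Reaching 11.8% needs three of 14 participants shifted the same way by 1.5 SD each.

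Finally, with opioids and other NSAIDs restricted, leaving one analgesic available looks deliberate, and therapies are reviewed at both draw visits. Both points are fair. They argue for keeping ibuprofen and using the records. They do not supply an interval or a planned listing.

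**Conclusion.** The point holds as a minor one. Ibuprofen is exempt by name and no fixed ibuprofen-free interval precedes either CRP and ESR draw. Cover at baseline is left to the QI's discretion, and at Day 140 it is unclear. If ibuprofen or its indication affects the markers, use near one draw only could move that participant's change in either direction without appearing in any planned output, although the visit records might reveal it afterwards.

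The size is not given and may be nil or small. Under the assumptions above, one affected participant does not raise total error, and shifts that offset one another keep it below 5%. Material inflation needs several participants shifted the same way by a large amount. The power losses matter mainly at shifts of 1 SD or more. Confidence is medium: the reading of the text is secure, but the consequence rests on assumptions that the documents cannot confirm.

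**What to change.** In the reminders before Visit 2 and Visit 8, ask participants to avoid ibuprofen for one stated interval, the same for everyone and for both draws. Three days is offered as an assumption for the QI to confirm, with the existing 14 days as the ceiling.

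Keep ibuprofen available. If it is needed, participants take it, and date, dose and reason are recorded. At Day 140 the visit may be moved within the existing ±3-day window. State that such use is not prohibited medication and not grounds for withdrawal under Section 7.4, because needing prohibited medication leads to withdrawal and withdrawn participants are not replaced.

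List last ibuprofen use and its reason beside each CRP and ESR result. Any analysis without recent users should be labelled supportive only: it selects on post-baseline behaviour and cannot separate the drug from its indication. It also loses precision. The 95% CI half-width, t(0.975, n-1)/√n, grows from 0.577 SD at n = 14 to 0.604 at 13, 0.635 at 12, 0.672 at 11 and 0.715 at 10.

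The cost is one CRF item, one reminder line before two visits, one listing, and a brief limit on one analgesic.

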7.4 Early Withdrawal

Personal reasons

As stated in the Informed Consent Form, a participant may withdraw from the study for any reason at any time.

Removal by Qualified Investigator

Participant discontinuation should be considered at the discretion of the qualified investigator. The circumstances of any discontinuation must be documented in detail in the participant file and final report. If possible, the evaluations planned for the end of treatment will be carried out at the time when the participant is withdrawn from the study. A participant leaving the study prematurely will NOT be replaced by another. It is understood by all concerned that an excessive rate of withdrawals can render the study uninterpretable, thus unnecessary withdrawal of participants should be avoided.

Criteria for removal of participants from the study includes:

Clinical reasons

A participant may be withdrawn from the study if, in the opinion of the qualified investigator, it is not in the participant's best interest to continue. Any participant who experiences a serious adverse event (SAE) may be withdrawn from the trial at the discretion of the qualified investigator. A participant will also be withdrawn due to adverse events causing clinically significant illness or the need for prohibited medication(s) during the trial. Any female participant who becomes pregnant during the course of the trial will be withdrawn.

Protocol violation

Any participant found to have entered this study in violation of the protocol will be discontinued from the study at the discretion of the qualified investigator. This will include any participant found to have been inappropriately enrolled (did not meet eligibility criteria). Participant non-compliance includes failure to show up for study visits, failure to take the investigational product as directed, or refusal to undergo study visit procedures. Participants who are found to be taking prohibited medications or supplements without the knowledge of the qualified investigator will also be withdrawn. Any major protocol deviations (i.e. those that increase the risk to participants and/or compromise the integrity of the study or its results) will result in participant discontinuation.

8 INVESTIGATIONAL DIET

8.1 Investigational Diet (Nic's Keto Diet)

Dietary Requirements	Quantity (Qty)
Calories from fat	70%
Protein	25%
Carbohydrates	5% (less than 20g of carbohydrates per day)

8.2 Directions

Participants will be instructed to follow Nic's keto diet plan for 140 days. Clinic staff will instruct participants to record results from their ketone and glucose monitor for the determination of compliance. Participants daily caloric need will be assessed for each participant as 90% of their energy requirements for weight maintenance based on their calculated base metabolic rate (BMR) and an activity factor. Participants will be advised not to exceed 20 g of carbohydrate per day (up to 5% caloric intake) and to consume the remaining 70% of calories from fat sources and 25% from protein sources. In addition to Nic's Keto Diet e-book, participants will be provided with a book summary and guidelines of foods that can be consumed and those that should not be consumed will be provided to the participant.

